6.3.4 Full Physical Exam

The Investigator or qualified designee will perform a complete physical exam at screening period and the time points defined in the study schedule of assessments (Table 3). Clinically significant abnormal findings should be recorded as AEs during the trial.

6.3.5 Directed Physical Exam

For cycles that do not require a full physical exam as described in the schedule of assessments (Table 3), the Investigator or qualified designee will perform a directed physical exam as clinically indicated prior to trial treatment administration.

6.3.6 Vital Signs

The Investigator or qualified designee will take vital signs at screening, prior to the administration of each dose of trial treatment and at treatment discontinuation as specified in the schedule of study assessments (Table 3). Vital signs should include temperature, pulse, respiratory rate, oxygen saturation, weight and blood pressure. Height will be measured at screening only.

6.3.7 Eastern Cooperative Oncology Group (ECOG) Performance Scale

The investigator or qualified designee will assess ECOG status (Appendix 1) at screening, prior to the administration of each dose of trial treatment and discontinuation of trial treatment as specified in the study schedule of assessments (Table 3).

6.3.8 Pulmonary Function Tests

Full lung function tests assessments will be performed at screening, prior to the dosing of pembrolizumab as specified in the study schedule of assessments (Table 3).

6.3.9 Pregnancy Tests

Female patients of childbearing potential should have a negative serum pregnancy within 72 hours prior to receiving the first dose of study medication as specified in the study schedule of assessments (Table 3). Additional urinary pregnancy test would be performed in these patients at the start of each cycle of Pembrolizumab during the treatment period and at the Safety Follow-up visit.

6.3.10 Haematology, Biochemistry and Urinalysis (including, β -hCG†, PT, aPTT, fT3, fT4 and TSH)

All laboratory tests will be performed at screening and then certain assessments at every visit as defined in the schedule of study assessments (Table 3). Sample will be analysed by the local study site laboratory using standard methods for routine tests. Laboratory tests for screening can be performed within 10 days prior to the first dose of treatment. After this all pre-dose laboratory procedures should be conducted no more than 72 hours prior to dosing. Results must be reviewed by the investigator / designee and found to be acceptable prior to each dose of trial treatment. The variables detailed in Table 4 will be measured.

Table 4: Required Laboratory Assessments

Haematology	Chemistry	Urinalysis	Other
Haematocrit	Albumin	Blood	PT
Haemoglobin	Alkaline phosphatase	Glucose	aPTT
Platelet count	Alanine aminotransferase (ALT)	Protein	Free triiodothyronine (fT3)
WBC (total and differential)	Aspartate aminotransferase (AST)	Specific gravity	Free thyroxine (fT4)
Red Blood Cell Count	Lactate dehydrogenase (LDH)	Microscopic exam (If results are abnormal)	Thyroid stimulating hormone (TSH)
Absolute Neutrophil Count	Uric Acid	Urine pregnancy test †	
Absolute Lymphocyte Count	Calcium Corrected		
	Chloride		
	Glucose		
	Phosphate		
	Potassium		
	Sodium		
	Magnesium		
	Total Bilirubin		
	Total protein		
	Blood Urea Nitrogen		
	Creatinine		
	Creatinine Clearance		
† Perform on women of childbearing potential only. If urine pregnancy results cannot be confirmed as negative, a serum pregnancy test will be required.			

6.3.11 Tumour Imaging and Assessment of Disease

6.3.11.1 Baseline tumour imaging

Imaging should be undertaken to confirm that the patient has disease in the thorax, where SBRT for pleural mesothelioma is considered appropriate and the lesion is measurable using mRECIST. The scan will also be assessed for extra-thoracic disease.

6.3.11.2 Timing of Disease Assessment

Tumour imaging will be performed by CT. The initial tumour imaging will be performed no more than 28 days prior to confirmation of eligibility. Scans performed as part of routine clinical management are acceptable for use as the screening scan if they are of diagnostic quality and performed within the correct time window.

On-study imaging will be performed at screening every 3 cycles (every 9 weeks) for the first 6 months (\pm 7 days) then every 12 weeks after 6 months (\pm 7 days), and should follow calendar days and should not be adjusted for delays in cycle starts or extension of pembrolizumab cycle frequencies. Tumour imaging and assessment per local standard of care should be performed for patient management and may include additional imaging (e.g. bone scan). Imaging should continue to be performed until documented disease progression, the start of new anti-cancer treatment, withdrawal of consent, death, or the end of the study, whichever occurs first.

6.3.11.3 Confirmation of Disease Response

Per modified RECIST (Appendix 6), response should be confirmed by a repeat radiographic assessment no less than 4 - 6 weeks from the date the response was first documented. The scan for confirmation of response may be performed at the earliest 4 - 6 weeks after the first indication of response, or at the next scheduled scan, whichever is clinically indicated.

Immunotherapeutic agents may produce anti-tumour effects by potentiating endogenous cancer-specific immune responses. The response patterns seen with such an approach may extend beyond the typical time course of responses seen with cytotoxic agents and can manifest a clinical response after an initial increase in tumour burden or even the appearance of new lesions. Therefore, modified RECIST may not provide an accurate response assessment of immunotherapeutic agents such as pembrolizumab.

Therefore, modified RECIST will be used with the following adaptations:

- If radiologic imaging shows initial progressive disease (PD), tumour assessment should be repeated 4-6 weeks later in order to confirm PD with the option of continuing treatment while awaiting radiologic confirmation of progression.
 - Patients may continue treatment while waiting for confirmation of PD if they are clinically stable as defined by the following criteria:
 - Absence of signs and symptoms indicating disease progression
 - No decline in ECOG performance status
 - Absence of rapid progression of disease
 - Absence of progressive tumour at critical anatomical sites requiring urgent alternative medical intervention. When feasible, patients should not be discontinued until progression is confirmed. This allowance to continue treatment despite initial radiologic progression takes into account the observation that some patients can have a transient tumour flare in the first few months after the start of immunotherapy, but with subsequent disease response. Patients that are deemed clinically unstable are not required to have repeat imaging for confirmation of progressive disease.

- If repeat imaging shows a reduction in the tumour burden compared to the initial scan demonstrating PD, treatment may be continued /resumed.
- If repeat imaging confirms progressive disease, patients will be discontinued from study therapy.
 - NOTE: If a patient with confirmed radiographic progression (i.e. 2 scans at least 28 days apart demonstrating progressive disease) is clinically stable or clinically improved, and there is no further increase in the tumour dimensions at the confirmatory scan, an exception may be considered to continue treatment upon consultation with the Sponsor (via RM-CTU). Clinically stable patients should also have at the confirmatory scan no further increase in the target lesions, no unequivocal increase in non-target lesions, and no additional new lesions develop (non-worsening PD) to continue study treatment.

In determining whether or not the tumour burden has increased or decreased, investigators should consider all target lesions as well as non-target lesions.

6.3.11.4 Confirmation of Disease Progression

Disease progression should be confirmed no sooner than 4 weeks after the first scan indicating progressive disease in clinically stable patients. Patients who have unconfirmed disease progression may continue on treatment until progression is confirmed.

Clinically stable is defined by one or more of the following criteria:

- Absence of signs and symptoms indicating disease progression
- No decline in ECOG performance status
- Absence of rapid progression of disease
- Absence of progressive tumour at critical anatomical sites (e.g., cord compression) requiring urgent alternative medical intervention

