6 STUDY PLAN AND PROCEDURES

6.1 Study Schedule

From study entry, patients will be assessed every 21 days, prior to the administration of each dose of pembrolizumab. During week 3 of SBRT for MPM, patients will have an additional clinical review. Patients will continue to be assessed and stay on pembrolizumab until they have disease progression, suffer unacceptable toxicities, withdraw, the study ends or have completed 35 cycles of pembrolizumab. Treatment beyond progression or 35 cycles needs to be discussed with the study sponsor and MSD. Patients will be required to attend a safety visit 30 days after their last dose of pembrolizumab.

If the patient has not progressed at the last dose of pembrolizumab they will be reviewed every 9 weeks until the start of new anti-cancer therapy, disease progression, death, withdrawal or end of the study. Patients that have progressed or begin a new anti-cancer treatment will enter into the survival follow up phase and an update will be sought every 12 weeks to assess for disease status until death, withdrawal of consent, or the end of the study, whichever occurs first. Survival follow up can be done over the phone.

The schedule of assessments to be performed at each visit is summarised in Table 3. Individual trial procedures are described in detail below. It may be necessary to perform these procedures at unscheduled time points if deemed clinically necessary by the Investigator. Furthermore, additional evaluations/testing may be clinically indicated for reasons related to patient safety. In some cases, such evaluation/testing may be potentially sensitive in nature (e.g., HIV, Hepatitis B, Hepatitis C, etc.) and will be performed in accordance with local regulations.

Table 3: Study Schedule of Assessments

Trial Phase:	Screening period	Initial phase			Maintenance phase DLT period (Pembrolizumab 200 mg q3wkly)			Maintenance phase ⁽¹⁰⁾ Beyond DLT period (Pembrolizumab 200 mg q3wkly)			End of Treatment (If applicable)	Post-Treatment				
		Radiotherapy phase (30 Gy 3#)			C2, D1	C3, D1	C4, D1	C5, D1	C6, D1	C7, D1	C8, D1	C X ¹⁰ , D1	Discontinuation of Pembrolizumab	Safety Follow- up (SFU)	Follow Up	Survival Follow Up
		C1, D1	C1, D15	C1, D17										30 days after last dose	Every 9 weeks from SFU	Every 12 weeks from SFU
Treatment Cycle/Title:					±3	±3	±3	±3	±3	±3	±3	±3	±3	±7	±7	±7
Scheduling (Day):	-28 to -1															
Informed Consent	X															
Inclusion/Exclusion	X															

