Patients who in the assessment by the Investigator, requires the use of any of the aforementioned for their clinical management should be removed from the trial. Patients may receive other medications that the investigator deems to be medically necessary. The Exclusion Criteria describes other medications, which are prohibited in this trial. There are no prohibited therapies during the Post-Treatment Follow-up Phase.

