7.8 Permanent Discontinuation of Trial Medication and Withdrawal from the Study

7.8.1 Permanent Discontinuation of Trial Medication

A patient may be permanently discontinued from the trial medication for any of the following reasons:

- The subject withdraws consent.
- Confirmed radiographic disease progression, please see Section 5.3.11.4.

Note: For unconfirmed radiographic disease progression. A patient may be granted an exception to continue on treatment with confirmed radiographic progression if clinically stable or clinically improved.

- Unacceptable adverse experiences
- Intercurrent illness that prevents further administration of treatment
- The patient has a confirmed positive serum pregnancy test
- Non-compliance with trial treatment or procedure requirements
- Administrative reasons
- Completion of 35 cycles of pembrolizumab

Trial patients will not be enrolled more than once. The primary reason for discontinuation should be recorded on the CRF. Once the trial medication has been discontinued the patient should complete the end of treatment (if applicable) and safety follow-up visit procedures as listed in the schedule of study assessment (Table 3). After the end of treatment, patients will continue to be assessed for AE and SAE monitoring until completion of the safety follow up visit.

Follow-up actions for patient discontinuing the trial are as follows:

- All patients will be required to:
 - Attend a safety follow-up 30 days after their last dose of pembrolizumab,
- If a patient **progresses or begins a new anti-cancer treatment** they will be required to:
 - Undertake survival status assessments every 12 weeks until death, withdrawal of consent, lost to follow up or the end of the study.
- If a patient discontinues for reasons other than progression during treatment and **does not withdraw their consent to follow up** they will be required to:
 - Attend follow-up assessments every 9 weeks until disease progression, initiation of a new anti-cancer treatment death, end of the study. Information regarding post-study anti-cancer treatment will be collected if new treatment is initiated.

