7.9 Withdrawal from the Study

Patients have the right to discontinue study treatment any time for any reason, without prejudice to their medical care. Withdrawal from the study refers to discontinuation of both study medication and study assessments; this can occur at any time according to the following reasons:

- Patient decision
- Lost to follow-up
- Death
- Principle Investigator decision

Patients may withdraw consent at any time for any reason or have trial treatment stopped at the discretion of the investigator should any untoward effect occur. In addition, a patient may be withdrawn by the Investigator or the Sponsor if enrolment into the trial is inappropriate, the trial plan is violated, or for administrative and/or other safety reasons. When a patient discontinues/withdraws prior to trial completion, all applicable activities scheduled for the final trial visit should be performed at the time of discontinuation, these are listed in the schedule of study assessments (Table 3). Any AEs which are present at that time should be followed in accordance with the safety requirements outlined in Section 8.

Patients who a) attain a complete response or b) complete 35 cycles of treatment with pembrolizumab must discontinue and may recommence for additional 17 cycles upon subsequent disease progression. Retreatment should be discussed with the Chief Investigator, the Sponsor and MSD. Pembrolizumab retreatment will be allowed only if it is in the best interest of the patients and if any other proven effective therapeutic options are no available as per standard of care and based on the investigator criteria. Study related assessment and procedures should be as for the beyond Pembrolizumab Maintenance phase (see Table 3). Patients do not need to re-sign the consent form for restarting treatment, provided their consent is on the most up-to-date version of the Patient Information Sheet Consent Form. After discontinuing treatment following assessment of complete response, these patients should return to the site for a 30 days safety follow-up visit and then proceed to the follow-up period of the study.

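### Section 6.3.11.4 counts a patient as clinically stable on any one of four criteria and lets dosing continue through unconfirmed progression without a stability condition, contrary to Section 6.3.11.3

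*Protocol*

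**What the plan says.** Two adjacent sections of the Protocol govern treatment between a first scan showing PD and its confirmation.

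- **Section 6.3.11.3 (Confirmation of Disease Response):** "Patients may continue treatment while waiting for confirmation of PD if they are clinically stable as defined by the following criteria". Four criteria follow: no signs or symptoms of progression, no fall in ECOG status, no rapid progression, and no progressing tumour at a critical site that needs urgent other treatment. Patients judged clinically unstable need no repeat scan.
- **Section 6.3.11.4 (Confirmation of Disease Progression):** "Patients who have unconfirmed disease progression may continue on treatment until progression is confirmed". The same four criteria are then listed under a different rule: "Clinically stable is defined by one or more of the following criteria". Cord compression is given as the example for the critical-site criterion.

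Section 7.8.1 lists reasons for permanent discontinuation. The only one based on progression is "Confirmed radiographic disease progression, please see Section 5.3.11.4" (the section number printed there should be 6.3.11.4).

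**The concern.** The two sections give different answers to one treatment question: may this patient receive the next dose before progression is confirmed?

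Section 6.3.11.4 departs from Section 6.3.11.3 in two ways. First, its definition is met by any single criterion, so a patient who is deteriorating in three respects is still called stable. Second, its continuation sentence carries no stability condition.

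What is at stake is the safety of patients with true progression who are getting worse, and consistent handling across investigators. Section 6.3.11.4 permits dosing such a patient; it does not require it.

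**Working it through.** **1. The rules side by side**

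| Question | Section 6.3.11.3 | Section 6.3.11.4 |
|---|---|---|
| May dosing continue during unconfirmed PD? | Only if clinically stable | Yes, with no condition in the sentence |
| How many of the four criteria define stable? | List with no qualifier | At least one |

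**2. How many patterns count as stable**

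Four met/not-met criteria give 2^4 = 16 patterns.

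- At least one met: 16 − 1 = 15 patterns are stable.
- All met: 1 pattern is stable.

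These are logical patterns, not patient frequencies.

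**3. Which reading Section 6.3.11.3 intends**

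The word *all* is not printed there, but it is the only workable reading. If one criterion were enough, a patient with cord compression would be stable because ECOG status had not yet fallen. A patient would be unstable only by failing all four criteria at once, which would leave the section's separate provision for unstable patients almost empty.

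**4. Whether other text settles it**

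- Section 6.1: "Treatment beyond progression or 35 cycles needs to be discussed with the study sponsor and MSD". It does not say whether unconfirmed PD counts as progression.
- Trial Summary, main study procedures: treatment beyond progression may be considered where there is clinical benefit. The same gap applies.
- Section 6.3.7: ECOG status is assessed before each dose, but no action is tied to a decline.
- Section 7.3.1: a patient who "requires the use of any of the aforementioned for their clinical management should be removed from the trial". This may catch cord compression needing steroids, but not general decline.
- Section 7.9: a patient may "have trial treatment stopped at the discretion of the investigator should any untoward effect occur". This is a power to stop, not a rule.
- Section 6.3.11.3, closing note: separate conditions apply after confirmed PD, which is a later decision.

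None of these says which definition governs.

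**5. Exposure during the confirmation interval**

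Inputs: 200 mg every 21 days (Section 4.2); scans within ±7 days of schedule, here taken around Day 1 (Section 6.3.11.2); confirmation 4 to 6 weeks later (Section 6.3.11.3). No dose delay is assumed.

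Let *a* be the days from the first PD scan to the next dose: 0 to 7 or 14 to 20, which is 15 values. Let *c* be the day of the confirmatory scan: 28 to 42, also 15 values. Count the doses at *a*, *a* + 21 and *a* + 42 that fall before *c*, over 15 × 15 = 225 combinations.

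- *a* = 0 to 6: the second dose falls on day 21 to 27, always before *c*. This gives 7 × 15 = 105 combinations with 2 doses.
- *a* = 7: the second dose falls on day 28, before *c* in 14 combinations.
- *a* = 14 to 20: the second dose falls on day 35 to 41, giving 7 + 6 + 5 + 4 + 3 + 2 + 1 = 28 combinations.
- A third dose would fall on day 42 at the earliest, so never before *c*.

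Total: 105 + 14 + 28 = 147 combinations with 2 doses, and 225 − 147 = 78 with 1 dose.

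Scans "should follow calendar days and should not be adjusted for delays in cycle starts", so after earlier dose delays they can fall anywhere in a cycle. With *a* = 0 to 20, 2 doses fall in 210 of 315 combinations and 1 dose in 105. Using the ±3-day dosing window (Section 7.2.7), a third dose can fit only when it is brought forward and the confirmatory scan is at the late end.

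The exposure is therefore 1 × 200 = 200 mg or 2 × 200 = 400 mg.

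**The case against.** The strongest reply is that this is loose drafting rather than contradiction. Section 6.3.11.3 never says *all*. The continuation sentence in Section 6.3.11.4 follows a sentence about clinically stable patients and precedes the definition of that term, so a fair reader could carry the condition across. It is permissive, and nothing compels an investigator to dose an unwell patient. Section 6.3.11.3 itself also says that, where feasible, patients should stay on treatment until progression is confirmed, without repeating the stability condition in that sentence.

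Part of this stands. The first conflict does rest on the ordinary reading of an unqualified list, and the practical risk is limited by clinical judgement and the provisions listed above. But the preceding sentence in Section 6.3.11.4 concerns the timing of the scan. Carrying its condition into the next sentence only imports the one-or-more definition, so the fault remains. The sentence in Section 6.3.11.3 comes after that section's own stability condition, though it adds to the pull towards continuing.

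A second objection is that the dose count does not measure the defect, treats calendar combinations as equally likely, and counts a dose given on the day of the first scan, when the result may not be known. That is correct. Leaving out the same-day dose (*a* = 0) moves 15 combinations from 2 doses to 1: 147 − 15 = 132 with 2 doses and 78 + 15 = 93 with 1. The range of 1 to 2 doses is unchanged. The fractions are not probabilities.

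**Conclusion.** The concern holds. The definition and the continuation sentence in Section 6.3.11.4 are wrong as written, and no other provision decides between the two sections. The conclusion depends on reading the list in Section 6.3.11.3 as requiring all four criteria, the only reading that makes clinical sense.

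The size is modest. Any patient treated through unconfirmed PD receives typically 1 or 2 doses (200 to 400 mg) before the confirmatory scan, assuming no dose delay and confirmation within 6 weeks. That is not the excess caused by the wording; the protocol gives no figure from which the excess, or the number of patients affected, could be derived. For a clinically unstable patient no repeat scan is required under Section 6.3.11.3, so a permission that lasts until confirmation may have no clear end.

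The sample size and dose-limiting-toxicity rules are untouched. Progression-free survival in Section 9.1.2 already counts clinical as well as radiological progression, so no effect on the analysis is claimed.

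**What to change.** Make three wording changes in an amendment:

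1. Section 6.3.11.4: define clinically stable by *all of the following criteria*.
2. Section 6.3.11.3: write *as defined by all of the following criteria*.
3. Section 6.3.11.4: change the continuation sentence to *Clinically stable patients who have unconfirmed disease progression may continue on treatment until progression is confirmed.*

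An equally good route is to state the definition once in Section 6.3.11.3 and refer to it from Section 6.3.11.4; change 3 is still needed. While editing, correct the cross-reference in Section 7.8.1 to 6.3.11.4. The conditions for treatment after confirmed PD and the definition of progression-free survival should stay as they are.

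The cost is an amendment with no new procedures, data or patients. The downside is that an occasional patient with a symptomatic tumour flare would stop early, which is already the result under the natural reading of Section 6.3.11.3.
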